8.4.2 Lesion count

8.4.2.1 Change from Baseline in lesion count

At each visit, lesion counts will be summarized by treatment group, anatomical region, and lesion type. The following lesion types will be summarized:

- Abscesses
- Inflammatory nodules
- ANs
- Non-inflammatory nodules
- Draining tunnels (fistulas/sinus tracts)
- Non-draining tunnels (fistulas/sinus tracts)
- HS scars

Total lesion counts (ie, the total across all anatomical regions) will be summarized by visit and lesion type, treatment group, overall and by Baseline Hurley Stage. Summaries will also be presented for the change and percentage change from Baseline in lesion counts by anatomical region and total lesion counts by lesion type.

A line plot of the percentage change from Baseline in AN count over time by treatment group will be produced. Separate plots will also be produced for the percentage change from Baseline

in the abscess count, inflammatory nodules count, and draining tunnel count, respectively, over time.

In order to investigate the effect of intercurrent events and missing data handling on lesion count data, the following **additional** iterations of each of the aforementioned plots (percentage change in AN count, abscess count, inflammatory nodule count and draining tunnel count, respectively) will be presented, with corresponding summary statistics tables:

- Intercurrent events:
 - Participants who have experienced intercurrent events
 - Participants who have not experienced intercurrent events
- Missing data handling:
 - Observed lesion counts (i.e., non-imputation)
 - Imputed lesion counts

Lesion count data will be listed by treatment group and anatomical region and will show region-specific Hurley Stage and worst overall Hurley Stage for each participant and visit. The total count for each type of lesion, across all anatomical regions at each visit will be listed separately. For the total abscess count and total draining tunnel (fistula/sinus tract) count, the change from Baseline will be listed; for the AN count, the percentage change from Baseline will be listed.

8.4.2.2 AN count of 0, 1, or 2

The number and percentage of participants with an AN count of 0, 1, or 2 will be presented by treatment group and visit. The denominator for the percentage calculations will be the number of participants in each treatment group in the RS with non-missing data at each visit.

8.4.2.3 AN25, AN50, AN75, AN90, AN100

Categorical response variables AN₂₅, AN₅₀, AN₇₅, AN₉₀, and AN₁₀₀ are defined to be equal to 1 if %ΔAN is less than or equal to -25%, -50%, -75%, -90%, and -100%, respectively, and 0 otherwise. This definition is introduced for identifying participants who respond to the treatment (1 = responder, 0 = nonresponder). The definition of percentage change from Baseline is given in Section 8.2.1. AN₂₅, AN₅₀, AN₇₅, AN₉₀, and AN₁₀₀ response will be summarized using frequency tables by treatment group for each visit.

8.4.3 Flare by Week 16

See Section 8.2.1 for the derivation of AN count.

Disease flare by Week 16 is defined as at least a 25% increase in AN count with an absolute increase of ≥ 2 AN relative to Baseline is observed by Week 16. A participant's disease flare status (yes/no) will be determined at each visit.

The number of participants who experience at least 1 disease flare by Week 16 will be analyzed using a logistic regression model including a fixed effect for treatment, Hurley stage at Baseline, and Baseline antibiotic use. The odds ratio versus placebo, p-value (from Wald test), and CI will be calculated. Missing data will be handled as described in Section 4.2.1.2.

8.4.4 Flare relative to Baseline

See Section 8.4.3 for the derivation of flare.

Disease flare status will be summarized by treatment group and visit using frequencies and percentages. The denominator for the percentage calculations will be the number of participants with non-missing data in each treatment group. This summary will also include the number of participants with any flare in the Initial Period, Maintenance Period, and the combined Initial and Maintenance Period. A bar chart of percentage of participants with flare, by visit and treatment, will be presented.

In addition, for each participant, the number of flares during the Initial Treatment Period will be calculated and summarized by treatment group. A corresponding histogram summarizing the number of flares during the Initial Treatment Period will be presented.

8.4.5 Time to flare by Week 16

See Section 8.4.3 for the derivation of flare.

Time to flare (in days) during the Initial Treatment Period will each be calculated as:

Min (Date of first flare, Date of Week 16 visit) – Date of first dose of study medication + 1.
All visits in the Initial Treatment Period including unscheduled visits are considered.

Participants who discontinue study treatment without experiencing a flare prior to Week 16 Visit will be censored at the date of last lesion count assessment. Participants who reach the Week 16 Visit without experiencing a flare will be censored at the date of the Week 16 Visit. Participants who experience an intercurrent event prior to experiencing a flare will be treated as experiencing a flare at the date of the intercurrent event. Participants will be censored at Baseline if there is no Baseline lesion count assessment or no Post-Baseline lesion count assessment.

Time to flare will be estimated and presented using the Kaplan-Meier product-limit method for each treatment group.

Kaplan-Meier plots of time to flare will be presented by treatment group. In these Kaplan-Meier plots, the line will start at 0 and will increase over time, representing time to achieving the response.

The median time to flare, including the 2-sided 95% confidence interval, will be calculated for each treatment. Comparisons of bimekizumab vs placebo will be analyzed using a log-rank test stratified by Hurley Stage at Baseline and Baseline antibiotic use.

8.4.6 Time to flare by Week 48

See Section 8.4.3 for the derivation of flare relative to Baseline.

Time to flare (in days) during the combined Initial and Maintenance Treatment Period will be calculated as:

Min (Date of first flare, Date of Week 48 visit) – Date of first dose of study medication + 1.
All visits in the up to Week 48 including unscheduled visits are considered.

Flare will be defined relative to the Baseline visit. Participants who discontinue study treatment without experiencing a flare prior to Week 48 visit will be censored at the date of last lesion count assessment. Participants who reach the Week 48 Visit without experiencing a flare will be

censored at the date of the Week 48 Visit. Participants who experience an intercurrent event prior to experiencing a flare will be treated as experiencing a flare at the date of the intercurrent event. Participants will be censored at Baseline if there is no Baseline lesion count assessment or no Post-Baseline lesion count assessment.

Time to flare will each be estimated and presented using the Kaplan-Meier product-limit method for each treatment group.

Kaplan-Meier plots of time to flare will be presented by treatment group. In these Kaplan-Meier plots, the line will start at 0 and will increase over time, representing time to achieving the response.

The median time to flare, including the 2-sided 95% confidence interval, will be calculated for each treatment.

8.4.7 International Hidradenitis Suppurativa Severity Score (IHS4)

The IHS4 is a validated scoring tool to dynamically assess HS severity to be used both in real-life and clinical trials settings (Zouboulis et al, 2017). The determination of the IHS4 score requires counting the inflammatory nodules, abscesses and draining tunnels (fistulas/sinus tracts), making it straightforward to apply in both research and clinical practice and easy to use in conjunction with the HiSCR.

$$\begin{aligned} IHS4 = & (number \ of \ inflammatory \ nodules \times 1) + (number \ of \ abscesses \times 2) \\ & + (number \ of \ draining \ tunnels \ (fistulas/sinus \ tracts) \times 4) \end{aligned}$$

The IHS4 score will be derived based on observed component total lesion count data; in the case of missing component data, the IHS4 score will be missing.

The observed IHS4 score, change and percentage change from Baseline will be summarized by treatment group and visit. Missing IHS4 scores will be imputed using the multiple imputation procedure specified in Section 4.2.2.1, where IHS4 scores will be derived based on the imputed lesion counts.

The IHS4 scores will be categorized into 3 HS categories (mild HS: ≤ 3 , moderate HS: 4-10, severe HS: ≥ 11).

The number and percentage of participants in each category (mild, moderate, severe) will be presented by treatment group and visit. The denominator for the percentages will be based on the number of participants in the given treatment group and visit for which there are no missing data (OC).

Shift tables for the changes from Baseline in this scale will be presented for each post-Baseline visit by treatment group. The denominator for the percentages will be based on the number of participants in the given treatment group and visit for which there is no missing data for the change (OC).

8.4.8 HS-Physician's Global Assessment 6-point scale

The HS-Physician's Global Assessment is a validated 6-point scale that is used to measure improvement in inflammatory nodules, abscesses, and draining tunnels. The HS-Physician's Global Assessment scale is defined in [Table 8-4](#).

Table 8-4: HS-Physician's Global Assessment 6-point scale

Score	Rating	Description
0	Clear	No abscesses, no draining tunnels (fistulas/sinus tracts), no nodules
1	Minimal	No abscesses, no draining tunnels (fistulas/sinus tracts), no inflammatory nodules, presence of non-inflammatory nodules
2	Mild	No abscesses or draining tunnels (fistulas/sinus tracts), and less than 5 inflammatory nodules, or Single abscess or draining tunnel (fistula/sinus tract), and no inflammatory nodules
3	Moderate	No abscesses or draining tunnels (fistulas/sinus tracts), and at least 5 inflammatory nodules, or Single abscess or draining tunnel (fistula/sinus tract) in the presence of inflammatory nodules, or Between 2 and 5 abscesses or draining tunnels (fistulas/sinus tracts) with or without inflammatory nodules, up to 10
4	Severe	Between 2 and 5 abscesses and draining tunnels (fistulas/sinus tracts), with inflammatory nodules that are greater than 10
5	Very severe	More than 5 abscesses or draining tunnels (fistulas/sinus tracts)

The gradings will be derived on a participant-level basis (ie, across all anatomical regions) based on the following rules:

- Clear:
 - number of abscesses = 0;
 - number of draining tunnels (fistulas/sinus tracts) = 0;
 - number of inflammatory nodules = 0;
 - number of non-inflammatory nodules = 0;
 - number of non-draining tunnels (fistulas/sinus tracts) – no limit;
 - number of HS scars – no limit;
- Minimal:
 - number of abscesses = 0;
 - number of draining tunnels (fistulas/sinus tracts) = 0;
 - number of inflammatory nodules = 0;
 - number of non-inflammatory nodules ≥ 1 ;
 - number of non-draining tunnels (fistulas/sinus tracts) – no limit;
 - number of HS scars – no limit;
- Mild:

- number of abscesses = 0;
- number of draining tunnels (fistulas/sinus tracts) = 0;
- number of inflammatory nodules ≥ 1 and ≤ 4 ;
- number of non-inflammatory nodules – no limit;
- number of non-draining tunnels (fistulas/sinus tracts) – no limit;
- number of HS scars – no limit;

OR

- sum of number of abscesses and number of draining tunnels (fistulas/sinus tracts) = 1;
- number of inflammatory nodules = 0;
- number of non-inflammatory nodules – no limit;
- number of non-draining tunnels (fistulas/sinus tracts) – no limit;
- number of HS scars – no limit;

- **Moderate:**

- number of abscesses = 0;
- number of draining tunnels (fistulas/sinus tracts) = 0;
- number of inflammatory nodules ≥ 5 ;
- number of non-inflammatory nodules – no limit;
- number of non-draining tunnels (fistulas/sinus tracts) – no limit;
- number of HS scars – no limit;

OR

- sum number of abscesses and number of draining tunnels (fistulas/sinus tracts) = 1;
- number of inflammatory nodules ≥ 1 ;
- number of non-inflammatory nodules – no limit;
- number of non-draining tunnels (fistulas/sinus tracts) – no limit;
- number of HS scars – no limit;

OR

- sum of number of abscesses and number of draining tunnels (fistulas/sinus tracts) ≥ 2 and ≤ 5 ;
- number of inflammatory nodules ≤ 10 ;
- number of non-inflammatory nodules – no limit;
- number of non-draining tunnels (fistulas/sinus tracts) – no limit;
- number of HS scars – no limit;

- Severe:
 - sum of number of abscesses and number of draining tunnels (fistulas/sinus tracts) ≥ 2 and ≤ 5 ;
 - number of inflammatory nodules > 10 ;
 - number of non-inflammatory nodules – no limit;
 - number of non-draining tunnels (fistulas/sinus tracts) – no limit;
 - number of HS scars – no limit;
- Very Severe:
 - sum of number of and number of draining tunnels (fistulas/sinus tracts) > 5 ;
 - number of inflammatory nodule – no limit;
 - number of non-inflammatory nodules – no limit;
 - number of non-draining tunnels (fistulas/sinus tracts) – no limit;
 - number of HS scars – no limit

The number and percentage of participants at each level of the assessment scale (Clear, Minimal, Mild, Moderate, Severe and Very severe) will be presented by treatment group and visit. The denominator for the percentages will be based on the number of participants in the given treatment group and visit for which there are no missing data for the HS-Physician's Global Assessment.

Shift tables for the changes from Baseline in this scale will be presented for each post-Baseline visit by treatment group. The denominator for the percentages will be based on the number of participants in the given treatment group and visit for which there is no missing data for the change from Baseline in HS-Physician's Global Assessment.

The HS-Physician's Global Assessment will be listed by treatment group and participant at each visit.

8.4.9 High Sensitivity C-Reactive Protein (hs-CRP)

Concentrations of hs-CRP, changes from Baseline, and percent change from Baseline will be summarized by treatment group and visit, where percent change is calculated as

$$\text{Percent change from Baseline} = 100 \times \frac{\text{Post Baseline hs-CRP} - \text{Baseline hs-CRP}}{\text{Baseline hs-CRP}}$$

Summary statistics will include n, arithmetic mean, SD, median, Q1, Q3, minimum and maximum. For the ratio to Baseline, summary statistics will include n, geometric mean, geoCV, median, Q1, Q3, minimum and maximum.

The ratio to Baseline will be calculated as follows:

$$\text{Ratio to Baseline} = \text{hs-CRP at post-Baseline} / \text{hs-CRP at Baseline visit}$$

The ratio to Baseline will also be summarized by treatment group and visit.

For the hs-CRP data, measurements that are below the limit of quantification (BLQ) will be imputed with half of the lower limit of quantification (LLOQ) for the purpose of calculating summary statistics, changes from Baseline, and ratio to Baseline.

Concentrations of hs-CRP, changes from Baseline, and ratio to Baseline will be listed.

8.4.10 Initiation of systemic antibiotic rescue therapy

See Section 3.9 for the definition of a systemic antibiotic rescue therapy.

The number of participants that use rescue antibiotic therapy will be summarized by treatment group for each period.

8.4.11 Time to initiation of systemic rescue therapy in the Initial Treatment Period

See Section 3.9 for the definition of a systemic antibiotic rescue therapy.

Time to initiation of systemic rescue therapy (in days) during the Initial Treatment Period will be calculated as:

Min (Date of initiation of rescue therapy, Date of change in the dose/type of current antibiotic, Date of Week 16 visit) – Date of first dose of study medication + 1.

Participants who discontinue the study without initiating systemic rescue therapy prior to Week 16 visit will be censored at the date of discontinuation. Participants who reach the Week 16 Visit without initiating systemic rescue therapy will be censored at the date of the Week 16 Visit.

Participants will be censored at Baseline if there is no Post-Baseline visit.

Time to initiation of systemic rescue therapy will be estimated and presented using the Kaplan-Meier product-limit method for each treatment group.

Kaplan-Meier plots of time to initiation of systemic rescue therapy will be presented by treatment group. In these Kaplan-Meier plots, the line will start at 0 and will increase over time, representing time to requiring rescue therapy.

The median time to initiation of systemic rescue therapy, including the 2-sided 95% confidence interval, will be calculated for each treatment. Comparisons of bimekizumab vs placebo will be analyzed using a log-rank test stratified by Hurley Stage at Baseline and Baseline antibiotic use.

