3.9 Definition of an intercurrent event

Handling of intercurrent events is one of the key elements for the analysis of efficacy endpoints.

An intercurrent event is defined as receipt of systemic antibiotic rescue medication or discontinuation of study treatment due to an AE or lack of efficacy (See Section 8.2.2).

Receipt of systemic antibiotic rescue medication is defined as initiating any systemic antibiotic on or after Baseline for any reason (including in response to an AE). The only exception to this rule is if a participant randomized to the antibiotic stratum on a tetracycline antibiotic interrupts their stable dose of tetracycline antibiotic during the study and subsequently restarts the same tetracycline antibiotic as confirmed using the coded preferred term. The restarted dose and frequency of the antibiotic must be the same or lower than the regimen prior to the interruption.

The dates of an intercurrent event are as follows:

- For receipt of systemic antibiotic rescue medication: start date of the antibiotic
- For discontinuation of study treatment due to an AE or lack of efficacy: Last study treatment date + 17 days. Note: study treatment discontinuation includes study discontinuation.

The choice of 17 days is intended to capture the interval between dosing and lesion assessments (14 days), as well as the visit window (3 days).

An additional sensitivity analysis will be conducted where missing data due to COVID-19 will be considered an intercurrent event and will be imputed as a nonresponse at that particular visit. This will be identified when there are missing data at a visit that has been impacted by COVID-19 according the COVID-19 impact CRF page. The date of this intercurrent event will be the date of the impacted visit.

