8.4.12 Time to an intercurrent event in the Initial Treatment Period

See Section 3.9 for the definition of an intercurrent event.

Time to an intercurrent event (in days) during the Initial Treatment Period will be calculated as:

Min (Date of intercurrent event, Date of Week 16 visit) – Date of first dose of study medication + 1.

Participants who discontinue the study without experiencing an intercurrent event prior to Week 16 visit will be censored at the date of discontinuation. That includes participants who discontinue from the study for reasons other than Adverse Event and Lack of Efficacy.

Participants who reach the Week 16 Visit without experiencing an intercurrent event will be censored at the date of the Week 16 Visit. Participants will be censored at Baseline if there is no Post-Baseline visit.

Time to an intercurrent event will be estimated and presented using the Kaplan-Meier product-limit method for each treatment group.

Kaplan-Meier plots of time to initiation of systemic rescue therapy will be presented by treatment group. In these Kaplan-Meier plots, the line will start at 0 and will increase over time, representing time to intercurrent event.

The median time to an intercurrent event, including the 2-sided 95% confidence interval, will be calculated for each treatment. Comparisons of bimekizumab vs placebo will be analyzed using a log-rank test stratified by Hurley Stage at Baseline and Baseline antibiotic use.

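### The time-to-rescue formula in SAP 8.4.11 also stops at any dose change of the current antibiotic, including reductions, which Section 3.9 does not count as rescue (minor impact)

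*SAP*

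**What the plan says.** Sections 8.4.10 and 8.4.11 both open with the same pointer: "See Section 3.9 for the definition of a systemic antibiotic rescue therapy".

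Section 3.9 then gives three rules.

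- What counts: "Receipt of systemic antibiotic rescue medication is defined as initiating any systemic antibiotic on or after Baseline for any reason".
- Its date: "For receipt of systemic antibiotic rescue medication: start date of the antibiotic".
- One exception, for a participant in the antibiotic stratum who interrupts a stable tetracycline and restarts the same drug. The condition is: "The restarted dose and frequency of the antibiotic must be the same or lower than the regimen prior to the interruption".

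Section 8.4.11 calculates the time as the earliest of three dates, minus the date of first dose, plus 1. The three are the initiation of rescue, the Week 16 visit, and "Date of change in the dose/type of current antibiotic". Its censoring rule mentions only rescue: "Participants who reach the Week 16 Visit without initiating systemic rescue therapy will be censored at the date of the Week 16 Visit". The Kaplan-Meier line is described as "representing time to requiring rescue therapy". A median with 95% CI and a stratified log-rank comparison with placebo follow.

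The companion analysis in 8.4.12 has no dose-change term. Its formula begins "Min (Date of intercurrent event, Date of Week 16 visit" and relies on Section 3.9 for the event.

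**The concern.** The section imports one definition of rescue and then applies a formula with a wider stopping rule. Lowering the dose of an ongoing antibiotic is not the initiation of an antibiotic. If anything it points away from a need for rescue. Yet it stops the clock. Nothing in 8.4.11 says whether such a stop is an event or a censoring.

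At stake is agreement within one family of outputs. The rescue counts in 8.4.10, the time to intercurrent event in 8.4.12 and the Section 6.4 summary of antibiotics qualifying as intercurrent events all rest on Section 3.9 alone. The 8.4.11 curve, median and log-rank test can use a date that is not a rescue date, so they need not match the others. Two programmers could also give the same participant different times and different event status.

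**Working it through.** No figure in the plan can be reproduced here, so the check applies the date rules to assumed dates.

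**Inputs.** The formula and censoring sentence come from 8.4.11, the definition, date and exception from 3.9, and the companion formula from 8.4.12. First dose is Day 1, so date minus first dose plus 1 equals the day number. The Initial Treatment Period is 112 days (Section 10.1.1.2), so the nominal Week 16 time is 112 + 1 = 113. The days of dose change and rescue are assumed.

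**Which part of the term is extra?**

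- A change of type to another systemic antibiotic is normally already an initiation under 3.9, so it adds little.
- A tetracycline restarted at a higher regimen fails the 3.9 exception and can also count as rescue.
- What remains is a dose change on the same drug that 3.9 does not capture. This includes every reduction and the exempted lower-dose restart.
- An antibiotic started after Baseline is already rescue at its start date, so a later dose change cannot come first. Only participants on an antibiotic at Baseline are affected.

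**Case A: reduction on Day 30, or tetracycline restarted at a lower dose on Day 30, and no other antibiotic.**

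- 8.4.11 formula: min(30, 113) = 30.
- 8.4.11 censoring sentence: no rescue initiated, so censored at 113.
- 8.4.12, with no intercurrent event: censored at 113.
- Gap: 113 − 30 = 83 days.

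**Case B: reduction on Day 30, new systemic antibiotic on Day 60.**

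- 8.4.11 formula: min(30, 60, 113) = 30.
- Section 3.9 rescue date: 60.
- 8.4.12: min(60, 113) = 60.
- Gap: 60 − 30 = 30 days.

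Rescue is one component of the intercurrent event, so time to intercurrent event can never exceed time to rescue. Case B gives 60 against 30. If the Day 30 stop is coded as an event, the curve shows a rescue before any occurred. If it is coded as a censoring, the true rescue on Day 60 is lost.

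**Scale.** The SAP gives neither the size of the antibiotic stratum nor how often doses were lowered. Purely as an assumption, take 10–30% of each arm in the stratum and 5–10% of those with a reduction by Week 16:

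| Arm | Low | High |
|---|---|---|
| Q2W, N=280 | 280 × 0.10 × 0.05 = 1.4 | 280 × 0.30 × 0.10 = 8.4 |
| Q4W, N=140 | 0.7 | 4.2 |
| Placebo, N=70 | 0.35 | 2.1 |

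These counts show an order of magnitude only. The conflict in Cases A and B does not depend on them.

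**The case against.** The best defence is that 8.4.11 can be read as a whole. It imports 3.9 with its tetracycline exemption, censors at Week 16 anyone who has not started rescue, and describes the curve in terms of needing rescue. On that reading Case A is censored at 113. It works, however, only by giving one of the three terms in the formula no effect for a reduction.

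A second defence is that the term was meant to catch escalation. That is plausible: one of the subgroups in Section 4.8 is defined by the start or increase of systemic antibiotic therapy after randomization. But there the direction is stated, and in 8.4.11 it is not. The amendment log does not settle the intention. Amendment 1 dropped the term from the intercurrent-event formula and kept it in the rescue formula, which fits either a leftover or a deliberate choice.

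Parts of the defence stand:

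- A reader might infer that dose and type changes are both new triggers. Type change is normally covered by 3.9 already.
- A reader might count an interruption as a dose change, so that a tetracycline stopped on Day 20 and restarted on Day 30 gives 20. The text does not say so.
- Deletion does lose something: an uninterrupted dose increase that 3.9 misses is no longer timed here.

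**Conclusion.** The point holds as a wording error with small reach. The formula in 8.4.11 can return a date that the section's own definition does not treat as rescue. It then contradicts the section's censoring sentence (30 against 113 in Case A) and can precede the 8.4.12 time (30 against 60 in Case B). Both results follow from the text once the example days are assumed.

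A reader might go on to infer a threat to the main results or a loss of power. The documents support neither. The primary and secondary endpoints use the Section 3.9 intercurrent event, not this formula. The analysis lies outside the testing hierarchy of Section 4.5 and is not among the nominal tests of Section 8.5. The number of participants affected cannot be derived from the SAP, so no power figure can be given.

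**What to change.** Delete the dose/type-change term from 8.4.11, so that time to rescue = Min (Section 3.9 rescue date, date of Week 16 visit) − date of first dose of study medication + 1. This agrees with 8.4.10, 8.4.12 and the Section 6.4 summary. Leave Section 3.9 unchanged, since it governs the primary and secondary endpoints.

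If the sponsor wants to see escalation of an ongoing antibiotic, report it as a separate supportive summary. Keeping the term in 8.4.11 but limiting it to increases would not do: an increase outside 3.9 would again be an event here but not in 8.4.10 or 8.4.12.

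The cost is one deleted term and no new data. The only loss is the timing of uninterrupted dose increases, which the supportive summary can cover.
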